3. SUBJECT SELECTION, RECRUITMENT, AND INFORMED CONSENT

PCP Selection, Recruitment, and Informed consent

Primary care providers (PCPs) specializing in internal medicine or family medicine with at least one half day per week outpatient clinic will be included in the study. We

estimate a total maximum recruitment of 80 eligible PCPs from all sites (approximately 50 PCPs from UI Health and MSHC sites and approximately 30 PCPs from CCHHS). The recruitment will include a combination of paper letter and email invitations with endorsement from the clinic directors and other supervisors. A list of eligible PCPs will be obtained from each site from the clinic directors. A research introduction letter will be mailed to the qualifying practitioners as well as an email invitation sent to their email accounts. The letter and email will be sent simultaneously to ensure contact and will include a short introduction to why the research is being performed and a description of participants' roles in the study. Also included will be a contact number for those who would like to volunteer or who would like additional information. The letter will include a statement that there will be no penalty for not participating. The letter will also contain a postcard with a stamp, where the eligible PCP checks to agree to participate or decline to participate. The email will instruct them to reply by email to the same choices. If a response is not received in 2 weeks, a second recruitment letter and email will be sent followed by a postcard 2 weeks later. Once a PCP agrees to participate, informed consent will be obtained prior to initiation of any study procedures.

Patient Selection, Recruitment, and Informed consent

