Approximately 500 patients will be recruited for this study from the FM, AIM, MSHC and GIM sites (A total of 250 from UI Health and MSHC sites and a total of 250 from CCHHS site). All sites use the same electronic medical record (EMR) system which is Cerner Powerchart. An Information Systems Specialists (ISS) from UI Health (including MSHC) and CCHHS will search the administrative data of their respective sites to provide a list of patients meeting the first three of the inclusion criteria listed above and are scheduled to be seen in PCP clinics or the CRC (Clinical Research Center at UIC), two weeks in the future. More specifically, using electronic health records, within the past 12 months, the following patients will initially be identified: age \geq 40 years and using at least one maintenance respiratory medication (e.g. long acting beta agonists (LABA), long acting anticholinergics (LAA), inhaled corticosteroids (ICS), phosphodiesterase-4 inhibitors (PDE-4i), and at least one of the following 1) diagnosis of asthma (ICD-9 493.xx or ICD 10 J45.xx), 2) diagnosis of COPD, emphysema, or chronic bronchitis (ICD-9 491.xx, 492.xx, 496 or ICD 10 J41.xx, J42.xx, J43.xx, J44.xx). In addition, our ISS will also only include those who have not had a current procedural testing (CPT) codes for spirometry (CPT codes: 94010, 94014, 94015, 94016, 94060, 94070, 94620) or completed order for spirometry testing in the past 3 years.

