4. DESCRIPTION OF PROCEDURES

A) PCP Education and Randomization:

After obtaining PCP informed consent and prior to patient recruitment, a one hour educational session will be held for PCPs participating in the study. The purpose of this session is to provide education to PCPs about COPD, asthma, spirometry, and GOLD and GINA guidelines (GOLD=Global Initiative for Chronic Obstructive Lung Disease, GINA=Global Initiative for Asthma). The educational session will provide continuing medical education credit to those who attend. The learning objectives will be the following: 1) Review COPD and asthma disease definition, presentation, diagnosis and testing including spirometry, 2) be familiar with the GOLD and GINA guidelines and recommendations for therapy.

PCPs who consented to participate in the study and completed the education session will be randomized to have their patients who meet the study criteria receive the intervention or usual care.

B) Patient subject- Intervention:

On the day of the outpatient visit, subjects will be advised to arrive 90 minutes prior to their clinic visit in the same building as the clinic site or the CRC (Clinical Research Center at UIC). The following information will be collected and procedures will be performed:

1. Subject demographic and contact information
2. Co-morbid conditions
3. Smoking history
4. Medication history from patient and also from pharmacy used by subjects
5. A respiratory exacerbation history in the past year
6. Modified Medical Research Counsel (mMRC) dyspnea scale and COPD Assessment Test
7. Quality of life measures
8. Pre and post-bronchodilator (BD) spirometry
9. De-Escalation Spirometry Screener for patients de-escalating based on spirometry (See Based on spirometry findings)
10. De-Escalation Phone Script

Based on spirometry findings:

1. If the spirometry findings are consistent with COPD and/or asthma, the following will be provided to the provider and patient to have available during the clinic visit: a letter summarizing the interpretation of the findings using GOLD/GINA criteria with recommendations for initial guideline driven therapy based on GOLD/GINA guidelines. Subjects will be managed by their PCP thereafter.

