2. If the spirometry findings are normal, with approval from the PCP, will de-escalate respiratory medication therapy via a stepwise process and schedule patient back for a repeat pre and post bronchodilator spirometry within 1-2 weeks at the same time and place as the PCP clinic session. Again with the PCP approval, this deescalation and repeat spirometry can occur in 1-2 week intervals until all maintenance medications are discontinued as long as the pre and post spirometry continues to be normal. After each visit, the following will be provided to the provider and patient: a letter summarizing the interpretation of the findings using GOLD/GINA criteria with recommendations for initial guideline driven therapy based on GOLD/GINA guidelines, if appropriate. Subjects will be managed by their PCP thereafter.
3. All spirometry test results and the subject's assessment at the time of the test will be uploaded into the subject's electronic health record for future reference.

D) Outcome Measures:

1. Primary outcome:

- (i) Accurate classification of patient as having COPD and/or asthma
- (ii) All-cause and respiratory related, acute care outpatient visits, ED visits, and hospitalizations

2. Secondary outcome:

- (i) Appropriate use of respiratory medications based on guidelines
- (ii) Use of other diagnostic testing: ECG, echocardiograms, CT/CXR, stress testing, cardiac catheterization, other pulmonary function tests
- (iii) Initiation of guideline based therapy
- (iv) Quality of life measures

E) Data collection and follow-up

1) Baseline data collection obtained at visit zero (V_0), in addition to those listed under intervention and usual care:

- 1. Demographic data (gender, age, self-reported race)
- 2. SES related measures: median household income
- 3. Level of education
- 4. Type of health insurance or self-pay
- 5. Up to two emergency contacts information
- 6. List of current respiratory medications from subject's pharmacy and verification with patient
- 7. Co-morbidities
- 8. History of prior ED visits or hospitalizations in the past one year with associated cause
- 9. EQ-5D 5L +B Bolt-on
- 10. SF-36 short form
- 11. Social support survey

2) All subjects will have their medical charts reviewed every 3 months after the initial visit (MR_1 , MR_2 , MR_3 , MR_4) up to one year. These electronic medical chart reviews will be used to obtain follow-up data since last study contact.

- 1. Change in type of health insurance or self-pay

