5. STATISTICAL ANALYSES

All data will be stored in a secure, locked location. Data will be entered and managed through the Research Electronic Data Capture (REDCap). REDCap is a secure web-based application for building and managing online databases. REDCap is provided by

the CCTS Design Analysis Core. Data will be analyzed for clinical effectiveness using intention-to-treat principles.⁶⁹⁻⁷¹ For **Aim 1**, we will evaluate the misdiagnosis rates of the intervened and usual care groups separately at the first visit. Then compare rates between groups by using a generalized linear mixed model for binary outcome with two cluster levels, PCP and hospital, to account for the dependence within clusters. For the **Aim 2**, to investigate the impact of the misdiagnosis over time (4 time points: 0, 3, 6, 9, 12 months) on the quality of life and healthcare utilization, we will fit generalized linear mixed models with time, group, and their interaction as the main predictors. Two cluster levels, PCP and hospital, will be specified in the model to account for the dependence within clusters^{72,73} and an appropriate link function will be used for each outcome. Clinical important confounders will also be adjusted in the models. Before these analyses we will use descriptive statistics to describe the sample, and any assumption behind each statistical method will be examined during the analysis. A two-sided p-value less than 0.05 would be considered as statistical significance. All the analyses will be conducted by using SAS 9.2 (SAS Inst., Cary, NC).

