For **Aim 3: Costs**: The intervention costs for the study include the cost of the spirometry test, the time of the CHW/health promoter, and time of pulmonologist to provide periodic oversight of spirometry validity. In addition to estimating the costs associated with the intervention it will be important to measure the healthcare utilization for participants included in the study. It is possible that the intervention leads to use of other healthcare resources, particularly if the patient is determined to be free of respiratory disease. Therefore, we will measure both respiratory-related and overall healthcare costs. To measure these costs, we will determine overall healthcare utilization and apply unit costs to each of the events. Using chart reviews, we will examine healthcare utilization during the follow-up period. We will categorize healthcare utilization into either respiratory-related or all other healthcare use. We will apply standardized prices to each of the utilization components to estimate the overall and respiratory-related healthcare resource use during the study period. The standardize prices will be based on either the National Committee for Quality Assurance standardize price list for their relative resource use measure or Medicare reimbursement rates. For medications, we will rely on average wholesale price of medications to assign an average price to each of the COPD and asthma-related medications.

Cost-Effectiveness: The secondary outcome measures included in the study will be used to estimate the effectiveness to be used in the cost-utility analysis. We will use responses to the EQ5D to estimate patient utility and use that in calculation of quality-adjusted life-years (QALY). The area under the curve will be compared between the two groups and the difference will be the incremental effect used in the cost-utility analysis.

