Cost-utility analyses: We will evaluate the cost-utility of the intervention compared to usual care over the study period using recommended methods for cost-effectiveness analysis.⁷⁴ To compare the cost-effectiveness of the intervention to usual care, the findings are summarized into a ratio that provides the results in terms of the costs per unit of effect. We will calculate the difference in intervention costs and respiratory-related healthcare resource use between groups to determine the numerator of the ratio and the denominator will be the difference in QALYs in the cost-utility analysis. These incremental cost-effectiveness ratios (ICERs) will represent the cost per gain in QALYs for the intervention compared to standard care. As part of the cost-utility analysis we will evaluate the uncertainty associated with the ICERs. We will use bootstrapping

methods to generate confidence limits for the ICERs.^{75,76} We will display the results graphically on a cost-effectiveness plane and generate cost-effectiveness acceptability curves for the intervention compared to usual care.^{77,78} Cost-effectiveness acceptability curves display the probability of the intervention being cost-effective given various threshold values.⁷⁸ Thus decision-makers can identify a threshold value appropriate for their setting and determine the probability that the intervention will be cost-effective. We will also conduct sensitivity analyses that use the measure of overall healthcare utilization in calculation of the costs, as there may not be perfect specificity in identifying respiratory-related costs during the follow-up assessments and the intervention may lead to differences in non-respiratory costs.

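### Incremental cost is defined with no baseline adjustment stated, although prior-year utilization is collected and could sharpen the cost difference at almost no cost

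*Combined protocol and SAP*

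**What the plan says.** Section 5, Aim 3, defines the ICER numerator in one sentence: "We will calculate the difference in intervention costs and respiratory-related healthcare resource use between groups to determine the numerator of the ratio". The costs paragraph fixes the measurement window: "Using chart reviews, we will examine healthcare utilization during the follow-up period". Neither paragraph names a cost model, a covariate or any use of utilization before enrolment. The stated sensitivity analysis replaces respiratory-related with overall utilization and leaves the method of comparison unchanged.

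The relevant baseline data are collected. Section 4.E.1 lists "History of prior ED visits or hospitalizations in the past one year with associated cause" and the current respiratory medications, verified with the patient.

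Aim 2 is handled differently. For quality of life and healthcare utilization, "we will fit generalized linear mixed models with time, group, and their interaction as the main predictors", with PCP and hospital as cluster levels, and "Clinical important confounders will also be adjusted in the models". Aim 3 does not refer to those models.

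On design, section 4.A says that PCPs who consent and complete the education session "will be randomized to have their patients who meet the study criteria receive the intervention or usual care". No stratification or constraint on that randomization is described. In section 3 the investigators "estimate a total maximum recruitment of 80 eligible PCPs from all sites", and "Approximately 500 patients will be recruited for this study".

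**The concern.** Past acute care use is a natural predictor of future acute care cost, and baseline medications are a natural predictor of medication cost. If some PCPs happen to have high-use patients, or if PCPs from the two hospital systems fall unevenly between arms, the follow-up cost difference will partly reflect what was there before the intervention. In the one trial that is run, that part cannot be told apart from a saving or an added cost of REDEFINE unless baseline use enters the analysis.

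The numerator feeds every Aim 3 summary: the ICER, its bootstrap limits, the cost-effectiveness plane and the acceptability curve. The aims could also disagree. Aim 2 could report an adjusted utilization effect near zero while Aim 3 reports a cost difference from many of the same events. The point concerns the cost numerator only, not the QALY denominator.

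**Working it through.** The plan gives no cost SD, ICC, correlation or power for cost, so there is no stated figure to reproduce. What follows is a range under assumptions.

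**From the documents:** N = 500 patients; at most 80 PCPs; mean cluster size m = 500/80 = 6.25.

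**Assumed:** equal arms; ICC of 0 to 0.10; correlation r between prior-year use and follow-up cost of 0.2 to 0.7, taken as the same at patient and PCP level.

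**Step 1: chance imbalance at baseline.** The design effect is DE = 1 + (m − 1) × ICC. The SE of the arm difference in SD units is √(DE × 4/N).

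| ICC (80 PCPs) | DE | SE | 95% range | Chance of imbalance above 0.1 SD |
|---|---|---|---|---|
| 0 | 1.000 | 0.089 | ±0.175 | 26% |
| 0.05 | 1.262 | 0.100 | ±0.197 | 32% |
| 0.10 | 1.525 | 0.110 | ±0.216 | 37% |

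For example, at ICC 0.05: DE = 1 + 5.25 × 0.05 = 1.2625, and √(1.2625 × 4/500) = 0.100. With only 40 PCPs and ICC 0.10, the range is ±0.257 SD and the chance is 45%.

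**Step 2: carry-over into an unadjusted cost difference.** Carry-over is r × imbalance. At the edge of the 95% range with 80 PCPs and ICC 0.05 this is 0.3 × 0.197 = 0.06 SD, 0.5 × 0.197 = 0.10 SD, or 0.7 × 0.197 = 0.14 SD of cost.

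**Step 3: precision gained by adjustment.** The variance is multiplied by 1 − r² and the interval width by √(1 − r²). The equivalent unadjusted sample size is 500/(1 − r²).

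| r | Variance reduction | Interval width reduction | Equivalent N |
|---|---|---|---|
| 0.2 | 4% | 2% | 521 |
| 0.3 | 9% | 5% | 549 |
| 0.5 | 25% | 13% | 667 |
| 0.7 | 49% | 29% | 980 |

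**Step 4: check with skewed data.** In 4,000 simulated trials (80 PCPs, 500 patients, gamma-Poisson event counts, arbitrary prices, no true effect, mean patient-level r about 0.59), the unadjusted difference had SD 161 and correlated 0.67 with the baseline imbalance. Regression on the prior-year count gave SD 120 and correlation 0.09. Both estimators averaged about zero. The variance ratio was 0.56. That is below 1 − 0.59² = 0.65 but agrees with 1 − 0.67² = 0.55 to within rounding: the simulated PCP effect was shared by both years, so the arm means correlated more strongly than individual patients did.

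**The case against.** The text does not call the difference raw. A covariate-adjusted group effect is also a difference between groups, and the section appeals in general terms to recommended cost-effectiveness methods. A reader might infer that the sponsor decided to ignore baseline use. The documents do not support that; they are silent. What stands is that no adjustment is stated and that the Aim 2 adjustment is not extended to Aim 3.

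A reader might also infer that the cost result will be biased. Randomizing PCPs makes the unadjusted difference unbiased on average, and a bootstrap that respects the clusters would include chance imbalance in its limits. The carry-over in step 2, measured in standard errors, is simply r times the imbalance and is not separate evidence of harm. What remains is avoidable error in the realised trial and wider limits than necessary.

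One could go further and suspect that arm was known when patients enrolled, since section 4 gives different arrival times by arm. The documents do not establish this: they do not state when arm is revealed relative to patient consent.

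There are also fair reasons to expect a modest r. Baseline history covers ED visits and hospitalizations, whereas follow-up also records acute outpatient visits and diagnostic tests. The eligibility criteria exclude recent life-threatening respiratory failure and recent specialist care, which may narrow the range of prior respiratory use. Medication may be reduced under the intervention, so baseline medication cost may predict less well in that arm. These points argue for a smaller gain, not against adjusting: a weak covariate costs very little precision.

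**Conclusion.** The point holds as a worthwhile, nearly free improvement. Aim 3 states no adjustment of incremental cost for baseline predictors that the trial already collects. The consequence is lost precision and avoidable chance-imbalance error, not systematic bias.

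The gain could be minor (interval 2% to 5% narrower at r of 0.2 to 0.3) or substantial (13% at 0.5, 29% at 0.7). It rests on an assumed correlation, and the imbalance figures rest on an assumed ICC, equal allocation and the planned maximum of 80 PCPs. A reader might turn these figures into a gain in power or a narrower ICER interval. Neither follows: the plan sets no power for a cost comparison, and the ICER interval also depends on uncertainty in QALYs, which was not examined here.

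**What to change.** State in section 5, Aim 3, that incremental cost is the adjusted group effect, expressed as a difference in mean cost, from a regression of 12-month cost on:

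- group;
- prior-year ED visits and hospitalizations (respiratory-cause for the main analysis, all-cause for the overall-cost sensitivity analysis);
- baseline respiratory medication cost, from the baseline list with the same unit prices;
- hospital system (UI Health/MSHC or CCHHS).

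Account for PCP clustering. Refit the model in every replicate of a bootstrap that resamples PCPs within arm, since resampling individual patients could leave the limits too narrow. Report the unadjusted difference as a sensitivity analysis. Fix the model form and the covariates before costs are compared by arm.

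The cost is a paragraph of SAP text and slightly more programming within the bootstrap already planned. No new data are needed.

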1. RESEARCH DESIGN

This will be a cluster-randomized comparative effectiveness trial conducted of patients with a primary care provider (PCP) diagnosis of COPD and/or asthma seen in outpatient primary care provider clinics (i.e. Family Medicine, Miles Square Health Center, and Academic Internal Medicine) as well as the CRC (Clinical Research Center) at the University of Illinois Hospital and General Internal Medicine and Family Medicine Clinics

at Cook County Health and Hospitals Systems (CCHHS). Providers will be randomized and their patients who fulfill the inclusion criteria will receive the intervention or be in the usual care group. Adults with a clinician-diagnosed COPD and/or asthma at high risk for diagnostic error due to lack of spirometry will undergo the REDEFINE intervention or usual care based on the PCP randomization. Outcomes will be assessed every 3 months for up to one year.

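### The only confidence limits stated for Aim 3 are on the ICER, with no rule for bootstrap replicates whose QALY difference falls on both sides of zero

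*Combined protocol and SAP*

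**What the plan says.** Section 5, under the cost-utility heading for Aim 3, reduces the comparison to an incremental cost-effectiveness ratio.

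- **Numerator:** "difference in intervention costs and respiratory-related healthcare resource use between groups to determine the numerator of the ratio".
- **Denominator:** "denominator will be the difference in QALYs in the cost-utility analysis". The QALYs come from EQ-5D responses: "The area under the curve will be compared between the two groups and the difference will be the incremental effect".
- **Interval:** bootstrap "methods to generate confidence limits for the ICERs". The type of bootstrap and the resampling unit are not given.
- **Other displays:** "We will display the results graphically on a cost-effectiveness plane and generate cost-effectiveness acceptability curves". The curves "display the probability of the intervention being cost-effective given various threshold values", and the choice of threshold is left to decision-makers.
- **Horizon and size:** "Outcomes will be assessed every 3 months for up to one year" (Section 1) and "Approximately 500 patients will be recruited for this study" (Section 3), under at most 80 randomized PCPs.

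Net monetary benefit is not mentioned. Nothing says what to report if the QALY difference changes sign across replicates.

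**The concern.** A ratio can be given percentile limits only if its values can be put in a meaningful order. An ICER loses that order when its denominator changes sign. A negative ratio then covers both cheaper-and-better and dearer-and-worse. A positive ratio covers both dearer-and-better and cheaper-and-worse. The ratio also jumps from very large positive to very large negative as the QALY difference passes through zero.

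The sign of the cost difference is open too. The Aim 2 hypothesis expects lower utilization, while the cost text in Section 5 allows that the program may prompt other care, and the program itself costs money. All four quadrants of the plane are therefore possible.

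Aim 3 hypothesizes that the program will be cost-effective. If the QALY difference is small, the only confidence limits named for that aim would pool replicates with opposite meanings, and the analyst would have no prespecified alternative.

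**Working it through.** The documents contain no QALY, cost or power figure for Aim 3, so there is nothing to reproduce. The check has three parts.

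**1. Why the limits lose meaning.** Take four replicates with an illustrative cost difference of ±$300, a QALY difference of ±0.01 and a threshold of $50,000 per QALY (all assumed). Net benefit = 50,000 × ΔQALY − Δcost.

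| Δcost | ΔQALY | ICER | Net benefit |
|---|---|---|---|
| +300 | +0.01 | +30,000 | +200 |
| −300 | −0.01 | +30,000 | −200 |
| −300 | +0.01 | −30,000 | +800 |
| +300 | −0.01 | −30,000 | −800 |

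The ICER takes two values for four different situations, and each value pairs a favorable result with an unfavorable one. Net benefit ranks all four correctly.

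**2. How often this could arise.** Inputs:

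- From Section 3: about 500 patients and at most 80 PCPs, so 500/80 = 6.25 patients per PCP.
- Assumed: 250 per arm (the 250/250 split in Section 3 is by site, not by arm), QALY SD 0.20, ICC 0.02.

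Design effect = 1 + (6.25 − 1) × 0.02 = 1.105.

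SE of the QALY difference = 0.20 × √(2 × 1.105/250) = 0.0188.

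More than 2.5% of replicates lie on each side of zero when the observed gain is within 1.96 × 0.0188 = 0.037 of zero. For a true gain d, the probability of that is

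1 − [Φ(d/SE − 1.96) + Φ(−d/SE − 1.96)].

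The range column varies the SD over 0.10-0.25, the ICC over 0-0.05 and dropout over 0-20%, which gives an SE of 0.009-0.027. The last column is a PCP-level cluster-bootstrap simulation (80 PCPs, 6 patients each, SD 0.20, ICC 0.02, 300 trials per setting).

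| True gain | d/SE | Formula, SD 0.20 | Range | Simulation |
|---|---|---|---|---|
| 0.01 | 0.53 | 92% | 80-93% | 90% |
| 0.02 | 1.06 | 81% | 39-89% | 79% |
| 0.05 | 2.66 | 24% | 0-55% | 24% |
| 0.08 | 4.25 | 1% | 0-17% | 1% |

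**3. What net benefit would and would not give.** Keep SD 0.20, ICC 0.02 and a threshold of $50,000. Add an assumed cost difference of $300 and a cost SD of $4,000, uncorrelated with QALYs.

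- SD of individual net benefit = √((50,000 × 0.20)² + 4,000²) = 10,770.
- SE of the difference = 10,770 × √(2 × 1.105/250) = 1,013.
- True net benefit is 500 − 300 = 200 at a gain of 0.01, and 1,000 − 300 = 700 at 0.02.
- The 95% interval includes zero in about 95% and 89% of trials respectively.

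The interval is ordered, but under these inputs it is usually inconclusive.

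**The case against.** The strongest reply is that Section 5 already handles the difficulty. It plans a cost-effectiveness plane and acceptability curves, and both remain valid when replicates cross zero. Each point on an acceptability curve is the proportion of replicates with positive net benefit at that threshold, so it speaks directly to the Aim 3 hypothesis. The text never calls the ICER interval the main result. This stands: a reader might infer that uncertainty goes unreported, and the documents do not support that. What remains is that a curve gives a probability, not an estimate with limits, and it does not repair the interval that the plan says it will produce.

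A second reply is that the failure may not occur. This also stands. A reader might infer that the ICER limits will usually be uninterpretable, but no expected QALY gain, SD or ICC is stated. The result depends heavily on the true gain: the problem is common at 0.02 or less and rare at 0.08.

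A third reply is that net benefit would not settle the question either. Part 3 of the working agrees. Inconclusiveness comes from limited precision, and changing the scale does not add precision.

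**Conclusion.** The point holds as a gap in prespecification. The plan puts its only stated Aim 3 interval on a ratio with an unprotected denominator and gives no fallback. If 250 per arm, a QALY SD of 0.20 and a design effect of about 1.1 are assumed, the limits would lose their meaning in roughly 80-90% of trials at a true gain of 0.01-0.02, about a quarter at 0.05 and about 1% at 0.08. Fewer PCPs or unequal arms would widen the QALY interval.

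The consequence is confined to one summary within Aim 3. The primary outcomes are untouched, and the plane and acceptability curves limit the damage. This is a worthwhile low-cost improvement, not a flaw that threatens the trial.

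**What to change.** Amend the cost-utility text in Section 5 along these lines:

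> Incremental net monetary benefit will be reported with a 95% bootstrap confidence interval at prespecified willingness-to-pay thresholds. The bootstrap will resample PCPs within arm and health system. The ICER will be reported as a point estimate, with confidence limits only if essentially all replicates have a QALY difference of one sign. The cost-effectiveness plane and acceptability curves will be presented as planned.

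Three details matter.

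- **State the share that counts as essentially all in advance.**
- **Set the condition on the sign of the QALY difference, not on a single quadrant.** Costs crossing zero do not disturb the ordering if every QALY difference has the same sign. With the part 3 inputs and a true gain of 0.08, about 83% of trials would have all 1,000 replicates on one side for QALYs, but only about 1% would have them all in one quadrant. A quadrant rule would suppress mostly valid intervals.
- **Resample PCPs.** Section 1 randomizes PCPs, and Section 5 models PCP and hospital clustering for Aims 1 and 2, but the bootstrap text does not mention clustering.

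The cost is SAP wording and a little programming. No new data are needed, and one set of replicates serves every display. The downsides are that the team must name thresholds in advance, and that the net-benefit interval may still include zero.
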